Study Protocol Title: Prospective randomized trial of Stratafix vs. Vicryl on operating room time and wound closure time in Total Hip Arthroplasty.

Protocol Version: 2.0

Protocol Date: 05/04/2018

Principal Investigator: [name], [contact], Email: [contact]

Funding Sponsor: Johnson and Johnson, Somerville, New Jersey

Project Contact:

[name], CCRA

Sr. Clinical Project Manager

Clinical Development

ETHICON, Inc. a Johnson & Johnson Company

P: [contact] F: [contact] Email: [contact]

Regulatory Sponsor:

This study is an Investigator Initiated research trial. Each study site will be considered its own regulatory sponsor and is responsible for internal data monitoring and any study reporting required by ClinicalTrials.gov.

Introduction:

Total hip arthroplasty is an effective orthopedic procedure to improve function, correct gait, and alleviate symptoms of late-stage arthritis in patients who have failed non-operative management. With constant introduction of various techniques for wound closure, assessment of closure times and outcomes will be a topic of marked importance.

The STRATAFIX (Ethicon, Johnson and Johnson, Somerville, New Jersey) Knotless Tissue Control suture device is a barbed suture that uses anchor technology to securely engage with the soft tissues while also eliminating the need for knots. The anchors, or barbs, are pressed out of the device core or formed within the core in a geometric pattern and arranged in a tapered manner to allow the device to pass through tissue in the direction toward the needle during closure. These knotless tissue control devices are deployed using a continuous technique, which we anticipate to be faster and more cost-effective than interrupted suturing.

Background and Significance/Preliminary Studies:

Preclinical and biomechanical studies have demonstrated efficacy in cosmetic skin and deep tissue closures.[1], [2] In addition, barbed sutures have been shown to provide water-tight closure and wound strength comparable to or superior to closure with conventional sutures. Many comparative studies have been published contrasting barbed sutures to conventional closure techniques in multiple surgical fields. [3], [4]

Various studies have evaluated the outcomes of different barbed suture devices, however there are no reports assessing the length of closure times using STRATAFIX (Ethicon, Johnson and Johnson, Somerville, New Jersey) Knotless Tissue Control Devices during deep closure in total hip arthroplasty. Stephens et al. [5] performed a prospective randomized study of 500 total knee arthroplasty patients who received either barbed suture (250) or conventional sutures (250) for deep closure of the surgical wound. The mean operating time was significantly shorter in the barbed group as compared to conventional group (64.3 vs 68.1 minutes, $p=<0.001$). In a study of 80 TKA (61 barbed, 19 conventional deep sutures) and 54 THA patients (37 barbed, 17 conventional deep sutures), Smith et al. [6] found significantly shorter closure time in the barbed suture group (16.78 vs. 26.5 minutes, $p<0.001$). One study reports one the use of Stratfix suture for intracorporeal suturing in myomectomy. Giampaolino et al. [7] performed a prospective randomized study on 47 patients and evaluated the mean operative time for

laparoscopic posterior myomectomy using Stratafix or conventional suture for intracorporeal suturing. There was a significant decrease in mean operative time associated with use of Stratafix suture as compared to conventional suture (66.3 vs 73 minutes, p=0.005).

This prospective randomized single-center study will examine the outcomes, mainly closure time, of deep closure during total hip arthroplasty using the STRATAFIX Symmetric PDS Plus (Ethicon, Johnson and Johnson, Somerville, New Jersey) barbed suture compared to interrupted VICRYL suture (Ethicon, Johnson and Johnson, Somerville, New Jersey).

Study Design:

In this prospective study examining the deep closure during total hip arthroplasty, active subjects will receive the STRATAFIX Symmetric PDS Plus (Ethicon, Johnson and Johnson, Somerville, New Jersey) suture while the control subjects will receive interrupted VICRYL suture (Ethicon, Johnson and Johnson, Somerville, New Jersey). Superficial closure will be the standard of care for both groups.

The purpose of this study is to compare end points (see below):

- **The primary endpoint** of the study will be closure time and operative time.
- **Secondary endpoints** will examine: wound complications, costs comparison between the two techniques.

Post-operatively, patients will be assessed at clinic visits at 6 weeks and 3 months. At these time points, we will assess (**Table 1**):

Table 1.

REQUIRED STUDIES	Pre-Op	Intra-operative	6 week post-op	3 month post-op
Informed Consent	x			
Length of surgery time		x		
Length of closure time		x		
Amount of suture material used		x		
Surgeon experience level		x		
Wound complications			x	x

Methods

- A prospective randomized pilot study

Sample

- 60 subjects for a pilot study

Inclusion Criteria:

1. Males and females, between the ages of 18 to 80 years at the time of signing the informed consent document.
2. Understand and voluntarily sign an informed consent document prior to any study-related assessments/procedures are conducted.
3. Able to adhere to the study visit schedule and other protocol requirements.
4. Able to fluently speak and understand the local language
5. If female, is non-pregnant (negative pregnancy test results at the baseline/randomization visit) and non-lactating.
6. End-stage osteoarthritis patients planning to undergo primary total hip arthroplasty
7. BMI less than 40 kg/m²

Exclusion Criteria:

1. BMI greater than or equal to 40 kg/m².
2. History of known bleeding disorder.
3. History of medical co-morbidity that may result in poor wound healing (i.e. diabetes mellitus, peripheral vascular disease).
4. Patients <18 or >80 years of age.
5. Patients who are prisoners.
6. Mentally unable to sign informed consent.
7. Has an uncontrolled illness that, in the opinion of the investigator, is likely to cause the patient to be withdrawn from the trial or would otherwise interfere with interpreting the results of the study.

Screening and Recruitment: Informed Consent

Informed consent will be obtained by one of the study coordinators/co-investigators during a clinical visit prior to procedure in the privacy of an examination room or an office. Patients will be informed about the study and inquired about their interest to participate. A consent document will be given and key parts of the research study will be explained in lay-terms to the patient to ensure full understanding. Any questions regarding the research study

will be answered at that time. It will be emphasized that participation is voluntary. Those patients who are willing to participate will be asked to sign the consent document along with the consenting researcher. A signed copy of the consent document will be handed to the patient while another copy is kept in their study file.

In the event that an approach prior to the day of surgery is not feasible, same day of procedure consenting will be attempted. Patients will be contacted by telephone (see phone script), and those interested in participating in the study will be informed about what is involved, the follow-up visit, and that participation in the study is strictly voluntary, and will not affect the scheduling of their upcoming surgery. If the patient is interested in participating, the patient can be either mailed or emailed a copy of the informed consent form, and then arrangements will be made to complete the informed consent process prior to the patient being taken back into the preoperative area on the day of surgery. The patient will be asked to come to the hospital on the day of surgery earlier than the time they were told to arrive by surgical scheduling in order to make sure there will be adequate time to discuss the study, including what is involved, risks, benefits, and alternatives. We do not believe that an eventual approach on the same day of procedure would represent an added stress for the patient or delay the start of the procedure. Similar to obtaining informed consent prior to the day of procedure, the process will occur in a private setting with ample time to discuss the study's implications, risks, benefits, and alternatives. No procedures or tests will be conducted on the screening visit after consenting the patient.

Randomization procedures:

Patients will be randomized to either arm of the study as follows: sealed envelopes in a random order will be used to place study participants in either the barbed suture arm or in the traditional suture arm of the study. Patients will be randomized in a one to one ratio. At the commencement of each arthroplasty, a random envelope will be drawn which dictated the type of suture to be used, thus blinding the patients to the type of suture they received.

Research Procedure:

A standard posterior approach will be performed by the participating surgeons. For the traditional closure (control group), Abductor muscles will be repaired using Ethibond, and the deep fascia will be repaired using interrupted number 1 braided absorbable sutures (Vicryl, Ethicon; Johnson & Johnson, Somerville, NJ). The subcutaneous fat layer will be then closed with simple interrupted knots using number 2-0 braided absorbable sutures (Vicryl), followed by closure of the subcutaneous layer using a number 2-0 monofilament absorbable suture with inverted interrupted knots (Monocryl, Ethicon; Johnson & Johnson) followed by the use of steri-strips and adhesive (See table 2).

For the active arm of the study, wound closure will be performed in this fashion: abductor muscles will be repaired using Ethibond 2-0 (Excel MX69G), and STRATIFIX symmetric PDS Plus #1 will be used to close the fascia. (See Table 2). The subcutaneous fat layer will be then closed with simple interrupted knots using number 2-0 braided absorbable sutures (Vicryl), followed by closure of the subcutaneous layer using a number 2-0 monofilament absorbable suture with inverted interrupted knots (Monocryl, Ethicon; Johnson & Johnson) followed by the use of steri-strips and glue (See table 2).

Closure with the unidirectional barbed suture involves starting at the upper end of the wound and proceeded distally. At the ends of the wounds, the suture is backstitched toward the midpoint for further reinforcement before bringing the needle out through the skin; the suture is then cut flush with the tissue at its free end. With each throw, the leading end of the suture is pulled with only enough tension to engage the barbs with the surrounding tissue, thereby locking the wound edges into approximation. As with the traditional closure and in concordance with our routine protocol, barbed closures were finished with skin steri-strips and adhesive.

Table 2: Suture Type for Closure Following Total Hip Arthroplasty.

Layer	Control Group	Active Group
Muscle	Ethibond 2-0 (Excel MX69G)	Ethibond 2-0 (Excel MX69G)
Fascia	Vicryl #1 (J947H#1)	STRATIFIX (SXPP1A04#1)
Subcutaneous	Vicryl 2.0 (J945H 2-0)	Vicryl 2.0 (J945H 2-0)
Subcuticular	Monocryl 3.0 (Y496H)	Monocryl 3.0 (Y496H)

Skin	Steri-strips, glue (Standard of care)	Steri-strips, glue (Standard of care)
------	---------------------------------------	---------------------------------------

Patient Protection:

All data collection sheets will be de-identified. All patients will be assigned a study ID. All data collected will be entered into Excel sheet and stored on Cleveland Clinic secure computers. Only members of the study team (listed on the IRB application) will have access to protected health information of patients included in this study.

Safety Monitoring Plan

Procedural safety will be documented in this study through patient and surgeon reported adverse events. AEs will be documented for all cases in this study. An Unanticipated Problem involving risks to participants or others is any event that (1) is unforeseen, (2) caused harm or placed a person at increased risk of harm, and (3) is related to the research procedures.

An Adverse Event (AE) is any untoward or unfavorable medical occurrence, including any abnormal sign (for example, abnormal physical exam or laboratory finding), symptoms, or disease. Adverse events can encompass both physical and psychological harms. An Internal Adverse Event (AE) is an untoward medical occurrence, which occurs to participants in research conducted by Cleveland Clinic and/or Cleveland Clinic is the IRB of record. External Adverse Event (AE) is an untoward medical occurrence experienced by subjects enrolled at other institutions for the same study approved at Cleveland Clinic or a different study using the same study drug/device. A Serious Adverse Event (SAE) is any adverse experience that results in any of the following outcomes:

- Death
- A life-threatening experience
- Inpatient hospitalization or prolongation of existing hospitalization
- A persistent or significant disability/incapacity.
- A congenital anomaly/birth defect

- Important medical events that may not result in death, be life-threatening, or require hospitalization may be considered a serious adverse drug experience when, based upon appropriate medical judgment, they may jeopardize the patient or subject and may require medical or surgical intervention to prevent one of the outcomes listed in this definition.

An Unexpected Adverse Event means any AE not previously known or included in the current Investigator's Brochure, consent form or other risk information.

Related/Possibly Related means there must be reasonable evidence to suggest the event was caused by the drug, device or investigational intervention.

1. Internal Serious Adverse Events (events that occur to participants enrolled in research being conducted by Cleveland Clinic or when Cleveland Clinic is the IRB of record) must be promptly reported to the IRB using the IRB AE Report Form within 10 working days from discovery/awareness which meet any of the following criteria as assessed by the PI/Co-I:

- a) Serious, Unexpected and Related/Possibly Related.
- b) AE's determined to be occurring at a significantly higher frequency or severity than expected.
- c) Other Unexpected AE's, regardless of severity, that changes the risk benefit ratio of the study and results in changes to the Research Protocol or Informed Consent process/document.

All Internal SAEs are also reported at continuing review using the AE Summary Log.

2. External Serious Adverse Events (events experienced by subjects enrolled at other institutions for the same study approved at Cleveland Clinic or a different study using the same study device/drug) are reportable to the IRB using the IRB AE Report Form within 10 working days from discovery/awareness when:

- a. The External SAE report includes reasonable evidence as assessed by a central monitoring entity [Coordinating or Statistical Center, or a Data Safety Monitoring Board (DSMB) or Data Monitoring Committee (DMC)] that the event is Serious, Unexpected, and Related/Possibly Related AND places the subjects or others at a greater risk of physical or psychological harm than was previously known or recognized. This will require a change in the protocol and/or consent document.

b. External SAE reports provided by the Sponsor to the investigator indicating the event is Serious, Unexpected and Related/Possibly related but without reasonable evidence or DSMB/DMC determination of greater risk are not reportable to the IRB within the 10 day window. Without Sponsor evidence or assessment the implications of the event cannot be determined by the research team and therefore need not be reviewed. These SAE' shall be placed on the AE Summary log to be submitted at the annual continuing renewal.

3. DEATHS are to be reported to the IRB using the IRB AE Report Form according to the following guidelines:

a) Internal Death:

- Related/possibly related whether expected or unexpected – within 5 working days from discovery/awareness
- Not related and expected – at time of continuing review
- Not related and unexpected – at time of continuing review except cancer studies.
- Cancer: Not related and unexpected within 10 working days from discovery/awareness

b) External Death:

Related/possibly related and unexpected – within 5 working days from discovery/awareness not related whether expected or unexpected – at time of continuing review related/possibly related and expected – at time of continuing review

c) ALL Deaths are also reported at time of continuing review using the AE summary log.

4. Non-serious Adverse events (Internal and External) that are both Related/Possibly related and unexpected are reported on the AE Summary Log at time of continuing review to assess trends.

5. An IRB staff (a qualified, licensed practitioner assigned to this function by the IRB chair and IRB Executive Director) reviews Adverse Event Reports to determine whether they represent Unanticipated Problem Involving Risks to Participants or Others. Events that are assessed, by either the IRB Staff or Investigator, to place subjects or others at a greater risk of harm than was previously known or recognized, or changes the risk/benefit ratio of the study, or

requires a change in the protocol and/or consent document are referred to Full Board for review under Policy #70. Events that do not involve risk to Participants or Others or changes to the informed consent or protocol do not require further review. Investigators are informed of the determination and the IRB file is updated.

6. The AE Summary Log is reviewed by the IRB at the time of continuing review to identify trends in frequency and severity which may impact subject safety.

This study is an Investigator Initiated research trial. Each study site will be considered its own regulatory sponsor and is responsible for internal data monitoring and any study reporting required by ClinicalTrials.gov.

Data Analysis:

Unless otherwise indicated, all testing of statistical significance will be two-sided, and a difference resulting in a p-value of less than or equal to 0.05 will be considered statistically significant. Also, after each analysis, General Linear Models (GLM) will be used to control for possible confounders, including BMI, gender, age and ethnicity.

References:

- [1] A. Sull, S. Inceoglu, A. August, S. Gregorius, and M. D. Wongworawat, “Comparison of Barbed Sutures in Porcine Flexor Tenorrhaphy,” *HAND*, vol. 11, no. 4, pp. 475–478, Dec. 2016.

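### Operative time is a second uncorrected primary, and a difference in it that is absent from closure time would count as positive although the suture cannot have caused it

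*Combined protocol and SAP*

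**What the plan says.** All references are to the combined protocol and SAP.

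- **Title:** "Prospective randomized trial of Stratafix vs. Vicryl on operating room time and wound closure time in Total Hip Arthroplasty".
- **Study Design:** the primary endpoint "of the study will be closure time and operative time".
- **Table 1, intra-operative column:** "Length of surgery time" and, as a separate row, "Length of closure time". No start or stop point is given for either, and nothing says that the title, the endpoint and Table 1 mean the same interval.
- **Background:** the "single-center study will examine the outcomes, mainly closure time, of deep closure during total hip arthroplasty", so closure time carries the emphasis.
- **Table 2 (Research Procedure):** the control fascia entry is "Vicryl #1 (J947H#1" and the active entry is the barbed suture. The muscle, subcutaneous, subcuticular and skin rows are the same in both arms.
- **Randomization procedures:** allocation is 1:1. The envelope is drawn at the start of each arthroplasty, and only the patient is described as blinded.
- **Sample:** "60 subjects for a pilot study", with no SD, target difference or power.
- **Data Analysis:** "all testing of statistical significance will be two-sided, and a difference resulting in a p-value of less than or equal to 0.05" is the only decision rule. A general linear model then adjusts for BMI, gender, age and ethnicity. There is no multiplicity rule and no analysis of the time before closure.

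**The concern.** Operative time is the time before closure plus closure time. The suture is first used at the fascia, so any effect it has on operative time must pass through closure. If operative time differs between arms and closure time does not, the difference arose where the suture was not in use.

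The plan has no rule for that case. It names two primary times, applies 0.05 to each, and does not say whether one or both must be significant. A trial that is positive on operative time alone could be reported as showing that the barbed suture saves operating time. Because the team can know the arm from the start of surgery, a change of pace before closure is a possible cause as well as chance. The time before closure would be a natural check on this, and the plan does not use it.

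The three undefined names add to the difficulty. Pre-closure time can be obtained by subtraction only if closure is defined so that it lies inside the operative interval.

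**Working it through.** **Inputs.** From the documents: 60 patients at 1:1, so 30 per arm; two-sided 0.05 for each of two primaries; a cited knee-replacement difference of 68.1 - 64.3 = 3.8 min with 250 per arm and p<0.001. The plan's own sample size cannot be reproduced, because no SD, effect or power stands behind it. All SDs below are assumptions: pre-closure 8, 12 or 20 min and closure 4 min, taken as independent. As a rough guide, the knee study's p-value implies a total-time SD of at most 3.8 / (t × sqrt(2/250)) = 12.8 min, where t is the two-sided 0.001 point on 498 df. That is a different operation.

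**1. False positives with no suture effect.** If the two tests were independent, the chance of at least one would be 1 - 0.95² = 9.75%. Operative time contains closure time, so the tests are correlated. A simulation (40,000 trials per setting, t-tests, 30 per arm) gave:

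| Pre-closure SD (min) | Operative time significant | Closure time significant | Either | Operative time only |
|---|---|---|---|---|
| 8 | 5.1% | 5.0% | 9.2% | 4.2% |
| 12 | 5.0% | 5.1% | 9.5% | 4.5% |
| 20 | 4.9% | 4.9% | 9.4% | 4.5% |

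Each test alone holds at about 5%. The excess is the last column, which is the result that the suture cannot explain. Removing it returns the total to the closure-time rate (for example, 9.2% - 4.2% = 5.0%). Among the trials where operative time was falsely significant, the pre-closure difference was itself significant in 57%, 70% and 81%.

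**2. Change of pace once the arm is known.** Suppose pre-closure time shifts by 3 min in one arm (an assumed size) and the suture has no effect. The SE of the operative-time difference is sqrt(SD_pre² + 4²) × sqrt(2/30), and the rejection rate is Φ(3/SE - 1.96) + Φ(-3/SE - 1.96).

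| Pre-closure SD (min) | Operative-time SD (min) | SE (min) | Rejection rate |
|---|---|---|---|
| 8 | 8.94 | 2.31 | 25% |
| 12 | 12.65 | 3.27 | 15% |
| 20 | 20.40 | 5.27 | 9% |

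**3. What chance variation before closure does cost.** For a true closure saving of 3.8 min, simulated power is about 95% on closure time (SE = 4 × sqrt(2/30) = 1.03 min). On operative time it is 37%, 21% and 11% at pre-closure SD 8, 12 and 20. The ratio of SEs, operative to closure, is 8.94/4 = 2.2, 12.65/4 = 3.2 and 20.40/4 = 5.1.

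**4. How sharp the negative control is.** The 95% CI half-width for the pre-closure difference is 2.00 × SD × sqrt(2/30) = 4.1, 6.2 and 10.3 min at SD 8, 12 and 20. By the formula in step 2, with SE = SD_pre × sqrt(2/30), a true 3-minute shift would be significant in about 31%, 16% and 9% of trials.

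**The case against.** The strongest reply is that randomization balances pre-closure time in expectation and that its variation is already in the standard error. This is correct. A reader might infer that chance before closure makes the operative-time test unreliable, and it does not: that test rejects in about 5% of null trials whether or not the interval is split. Nor is the frequency of a chance 3.8-minute difference a false-claim rate. At an SD of 12.8 min such a difference arises in about 25% of trials, but the smallest significant difference at 30 per arm is about 6.6 min, so it would not be declared. At an SD of 8 min the threshold is 4.1 min, still above 3.8.

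Two other readings go too far. One is that closure time is never separated. Table 1 records it in its own row and it is a named primary, so only an analysis of the remainder is missing. The other is that the title means room occupancy with anaesthesia and positioning. No section says so. The Background uses operating time and operative time alike for earlier studies, so loose synonyms are at least as likely. What stands is that none of the terms is defined.

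It can also be said that total operative time is a legitimate pragmatic endpoint in a pilot, and that readers will see both results side by side. That is fair, and operative time need not be removed. But the plan sets a significance rule for a pilot with two primaries and leaves the discordant case open. The control is also weak at this sample size, as step 4 shows, so it cannot carry the argument without the attribution rule.

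**Conclusion.** The point holds as one about attribution and a second uncorrected primary. An operative-time difference not mirrored in closure time cannot be a suture effect, because the arms differ only at the fascia, and the plan would still let it count. If either primary may count, about 9% to 10% of null trials are positive, of which 4% to 5% are on operative time alone. A 3-minute change of pace would take operative-time rejections to about 9% to 25%.

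These sizes depend on assumed SDs, on independent pre-closure and closure times, and on reading the two primaries as alternatives. If both had to be significant, the 9% to 10% would not arise, but the plan does not say so. The documents show that pace could change, since the arm can be known from the start of surgery; they give no evidence that it would. The remedy is a cheap improvement and does not mean that the operative-time test is invalid.

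**What to change.** 1. Use one term and one interval for operative time, from skin incision to completion of skin closure, in the title, the endpoint and Table 1.
2. Define the start and stop of closure so that closure nests within that interval. If closure means the deep layer only, operative minus closure time also contains the later layers and is not pre-closure time. Derive the control directly as incision to start of closure.
3. Report the between-arm difference in that time, with a 95% CI, as a pre-stated negative control. Add that a non-significant result at 30 per arm does not show that bias is absent.
4. State that an operative-time difference is attributed to the suture only to the extent that it appears in closure time.

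The cost is wording in the title, Study Design, Table 1 and Data Analysis, a recorded time for the start of closure, and one line of analysis. Table 1 already collects both durations. The small downside is that an operative-time difference standing alone can no longer be claimed.

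### Closure time and operative time share the primary endpoint, each testable at 0.05, with no success rule and no deciding analysis

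*Combined protocol and SAP*

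**What the plan says.** The endpoint list in Study Design uses a singular label for two outcomes: the primary endpoint "of the study will be closure time and operative time". Two other places bear on which of them leads, and they point in different directions. The last paragraph of Background and Significance describes the study's outcomes as "mainly closure time, of deep closure during total hip arthroplasty". The protocol title names both times and puts operating room time first.

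Data Analysis is two sentences long. The first makes all testing two-sided unless otherwise indicated and says that "a difference resulting in a p-value of less than or equal to 0.05 will be considered statistically significant". Nothing is indicated otherwise anywhere in the protocol. The second says that "after each analysis, General Linear Models (GLM) will be used to control for possible confounders". The analysis that comes before the GLM is not named, and neither analysis is said to decide. The covariate list is open-ended: "possible confounders, including BMI, gender, age and ethnicity". Table 1 also collects "Surgeon experience level", and Research Procedure says the approach "will be performed by the participating surgeons", but the plan does not say whether experience enters the model.

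Methods describes a pilot of 60 subjects, and Randomization procedures sets a 1:1 ratio, so 30 per arm. No power calculation, standard deviation or correlation between the two times is given.

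**The concern.** With two outcomes under one primary label and one threshold for every test, the plan does not define what counts as success. Suppose closure time gives p = 0.03 and operative time p = 0.30. An analyst could say that the primary endpoint was met, because one component was significant, or that it was not, because the other was not. Both statements would fit the text. Such a split is plausible, since a saving in fascial closure may be diluted within the whole operation.

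The two readings have different costs. If one significant time is enough, the chance of a false claim exceeds 0.05 when the suture affects neither time. If both are needed, the error is controlled, but the trial succeeds only if operative time, the outcome in which a closure effect is likely to be hardest to see, also reaches significance.

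The same gap exists one level down. Each time will have a base result and a GLM result, and nothing says which one is the answer if they fall on opposite sides of 0.05.

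**Working it through.** **Nothing to reproduce.** The threshold of 0.05 is a choice, no overall error rate is stated, and the 60 subjects have no calculation behind them. The check therefore works out what each reading of the plan implies.

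**Inputs from the protocol.** Two primary times (Study Design); two-sided 0.05 for each test (Data Analysis); 60 subjects at 1:1, so 30 per arm (Methods, Randomization procedures). **Assumed:** the correlation r between the two test statistics, varied from 0 to 0.95.

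**Reading 1: either time suffices, and the suture affects neither.** For r = 0, the error is 1 − (1 − 0.05)² = 0.0975. For r > 0, it is 1 − P(|Z₁| < 1.96 and |Z₂| < 1.96), with (Z₁, Z₂) bivariate normal with correlation r. The chance that both are significant is 0.05 + 0.05 minus that figure.

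| r | at least one significant | both significant |
|---|---|---|
| 0 | 9.75% | 0.25% |
| 0.5 | 9.07% | 0.93% |
| 0.8 | 7.81% | 2.19% |
| 0.9 | 7.04% | 2.96% |
| 0.95 | 6.46% | 3.54% |

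Simulated two-sample t tests with 30 per arm (200,000 runs per setting) gave 9.8%, 9.1%, 7.0% and 6.5% at r = 0, 0.5, 0.9 and 0.95, in agreement.

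**Reading 2: both required.** If the suture fails to affect at least one time, a false success needs that time to be significant at 0.05, so the error is at most 5%. The cost is power. The protocol prints no standard deviation for operative time, but two studies summarised in Background and Significance allow an illustrative back-calculation, assuming t tests:

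- Knee study: difference 68.1 − 64.3 = 3.8 minutes, 250 per arm, p < 0.001. The critical t (498 df) is 3.31, so the standard error is at most 3.8 / 3.31 = 1.148, and SD ≤ 1.148 / √(2/250) = 12.8 minutes.
- Myomectomy study: difference 73 − 66.3 = 6.7 minutes, 47 patients (arms of 23 and 24 assumed), p = 0.005. Here t (45 df) is 2.952, the standard error is 6.7 / 2.952 = 2.27, and SD = 2.27 / √(1/23 + 1/24) = 7.8 minutes.

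Power for a 3.8-minute difference with 30 per arm, two-sided 0.05 (58 df), has non-centrality 3.8 / (SD × √(2/30)):

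- SD 12.8: 3.8 / 3.305 = 1.15, power about 20%.
- SD 7.8: 3.8 / 2.014 = 1.89, power about 46%.

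The power to win on both times cannot exceed these values.

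**Choice of analysis.** With closure time as the only primary outcome and no true effect, claiming whichever of the unadjusted or GLM result is significant gave about 6% to 8% in simulation. The settings were 30 per arm, four or five covariates, and assumed covariate R² of 0.05 to 0.3. The R² values are not from the protocol, so this figure is illustrative only.

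**Error under the possible rules.** With a fixed order, operative time is tested only after closure time is significant, so the familywise error is at most 5%. Holm with no effect on either time gives 4.94%, 4.65%, 4.02% and 3.30% at r = 0, 0.5, 0.8 and 0.95.

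**The case against.** The strongest reply is that the inflated error belongs to a reading the protocol never adopts. The endpoint label is singular and the two times are joined by a conjunction, so requiring both is at least as natural, and on that reading the error is at most 5%. This stands. A reader might infer that the plan permits a claim on either time, or that its true error rate is 6.5% to 9.75%. The text supports neither; it only fails to rule them out.

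The inflation also needs the suture to affect neither time. The Introduction describes continuous closure as a technique "which we anticipate to be faster and more cost-effective than interrupted suturing", and the clinical studies summarised in Background and Significance report shorter times. If closure time is truly shortened, only operative time can be falsely claimed, and that risk is 5%. This stands too, but it does not settle how a split result should be reported.

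A reader might go further and count four claimable tests, two times by two analyses. Nothing in the protocol says any of the four may be claimed. The GLM can reasonably be read as support for the first analysis, although it is not labelled so. Any error figure for four tests would rest on correlations and covariate strengths that the documents do not supply.

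It may be said that the wording in Background and Significance already puts closure time first. It leans that way, but it is narrative, and the title and the endpoint list do not follow it.

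Finally, this is a pilot, where strict error control matters less. That lowers the stakes. The plan nevertheless declares statistical significance, so it should say on what.

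**Conclusion.** The point holds as a missing decision rule. The plan lets each of two primary times be called significant at an unadjusted 0.05 without saying what combination counts as success, and it does not say which of two analyses decides.

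The size depends on the reading. If either time may be claimed and neither is affected, the familywise error is 6.5% to 9.75%, that is 1.3 to 1.95 times 0.05, for an assumed correlation of 0.95 down to 0. If both are required, the error is at most 5%, and success is limited by power for operative time of about 20% to 46% at a 3.8-minute difference. Those power figures borrow their standard deviations from other operations and assume t tests and near-equal arms. The 12.8-minute value is an upper bound, because the knee study reports only p < 0.001. They illustrate the trade-off and do not show that this trial is underpowered.

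This should be fixed before outcome data are examined. It does not undermine the design.

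**What to change.** State one success rule in Study Design. Any of three would do, and the choice is the sponsor's:

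- **(a) Closure time as the single primary endpoint**, with operative time tested at 0.05 only if closure time is significant. This fits the emphasis in Background and Significance. Cost: operative time cannot be claimed on its own.
- **(b) Holm across the two times**, if both stay primary as the title and the endpoint list suggest. The smaller p-value is tested at 0.025 and, if significant, the other at 0.05. Cost: the stricter first threshold.
- **(c) Both required**, each at 0.05. Cost: power is limited by operative time.

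In Data Analysis, name one deciding analysis: either a specified unadjusted comparison (for example, a two-sample t test) or the GLM. Label the other supportive. If the GLM decides, fix its covariate list before outcome data are examined and state whether the surgeon experience level collected in Table 1 is in it. Report both differences with 95% confidence intervals whatever the p-values, as suits a pilot.

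The change is a few sentences, with no extra patients and no new data items.
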